Appendix-II

DATA SCHEDULE

Title : Effects of vitamin D₃ supplementation on lung functions and exercise tolerance in D₃ deficient ACO patients .

SL No. :

ID No. :

Date :

Subject information:

Name :

Age :

NID No :

Contact address
:

Permanent
address :

Contact No : Patient:
Attendant:

Monthly income
(taka) :

No. of family
member :

Residence : Urban/Rural

Occupation : Homemaker-1, Student-2, Retired-3,
Business-4, Service-5, Day labourer-6

Education : Illiterate-0, Primary-1, High school-2, SSC-3,
HSC-4, Graduate-5, Masters-6

Marital status : Married-1, Unmarried-2, Widower-3,
Separated-4, Divorced-5, Livetogether-6

Biomass fuel : Yes/No
exposure

Smoking habit : Current/Past smoker
: Duration of smocking:
: Stopped for (in years, if past smoker):
: Packs-year: (sticks per day/20 X
year)

Past medical history:

H/O Hypertension	: Yes/No	If yes, duration	 months
H/O Diabetes mellitus	: Yes/No	If yes, duration	 hs
H/O Cardiac disease	: Yes/No	If yes, duration	 hs
H/O Renal disorder	: Yes/No	If yes, duration	 hs
H/O Endocrine disorder	: Yes/No	If yes, duration	 hs
H/O Psychosis	: Yes/No	If yes, duration	 hs
H/O Rheumatoid arthritis	: Yes/No	If yes, duration	 hs
H/O Other disease	: Yes/No	If yes, duration	 hs
Drug history	:		

History of ACO:

Place of diagnosis :

Duration of illness :

Features	Favors Asthma	Favors COPD
Age of onset	 Before age 20 years	 After age 40years
Pattern of respiratory symptoms	 Variation in symptoms over minutes, hours or days  Symptoms worse during night or early morning  Symptoms triggered by exercise, emotions including laughter, dust or allergen	 Persistence of symptoms despite treatment  Good or bad days but always daily symptoms & exertional dyspnea  Chronic cough & sputum preceded dyspnea, unrelated to triggers
Lung function	 Record variable airflow limitation (spirometry, peakflow)	 Record persistent airflow limitation (post BD <0.7)
Lung function between symptoms	 Normal	 Abnormal
Past history or family history	 Previous doctor diagnosis of asthma  Family history of asthma and other allergic condition	 Previous doctor diagnosis of COPD, chronic bronchitis or Emphysema  Heavy exposure to tobacco smoke, biomass fuel
Time course	 Symptoms vary seasonally, or from year to year  May improve spontaneously or have an immediate response to BD or to ICS over weeks	 Symptoms slowly worsening over time (progressive)  Rapid acting bronchodilator provides only limited relief.
Chest X-ray	 Normal	 Severe hyperinflation

History of sun exposure:

Time : /day or week or month

Duration : /min or hour

Anthropometric data:

Height : cm Weight: kg BMI: kg/m²

Waist: cm Hip: cm Waist-hip ratio:

MUAC: cm

General examination: (present = +, absent = -)

Anaemia - / + / ++ / +++

Jaundice - / + / ++ / +++

Cyanosis - / + / ++ / +++

Clubbing - / + / ++ / +++

Edema - / + / ++ / +++

Ascites - / +

Pulse rate :

(Beats/min)

BP : Systolic:

(mmHg) Diastolic:

Systemic

examination:

Respiratory system:

Shape of the chest : Normal-1;abnormal-2

Movement of chest : Abdominothoracic-1;
thoracoabdominal-2

Tracheal position : Central-1;shifted to right-2;
shifted-3

Use of accessory respiratory muscle : Yes-1;no-2

Percussion note : Dull-1;resonant-2

Breath sound : Vesicular-1;bronchial-2

Added sound : No-1;ronchi-2;creps-3

Other system:

Heart	:	Not palpable-1;palpable-2	
Kidney	:	Not palpable-1;palpable-2	
Spleen	:	Not palpable-1;palpable-2	
Liver	:	Not palpable-1;palpable-2	

Lung function test:

Variables	MV	% of PV	MV	%	of	MV	% of PV
	Day 1	Day 1	Day 90	PV		Day 90	Day 180
	(post		(post	Day		(post	
	BD)		BD)	90		BD)	

FVC(L)

FEV1(L)

FEV1/FVC(L)

PEFR(L/S)

FEF 25-75%

(PV =Predicted Value , MV=Measured Value) \

Exercise tolerance variables

(a) 6MWD	On day	On day	On day
(meter)	0	90	180

No. of laps.....(X 60 min)+ final
partial lap.....meter

Stopped or paused before 6min (yes/no)

Reason

Symptoms at the end of exercise:

angina/dizziness/hip,leg or cuff pain

	On day 0		On day 90		On day 180	
	Before 6MWT	After 6MWT	Before 6MWT	After 6MWT	Before 6MWT	After 6MWT
(b)(SpO2)(%)						

(c) Level of
dyspnea(score)

(d) Level of
fatigue(score)

Haematological variables:

Variables	On day 1	On day 90	On day 180
Serum 25(OH)D (mg/ml)			
Serum Ca ² (mg/dl)			
Serum PO ₄ ³⁻ (mg/ml)			
Serum PTH (pg/ml)			
Serum creatinine(mg/dl)			
Serum SGPT (U/L)			
Serum cholesterol (mg/dl)			
Serum TG (mg/dl)			
Serum HDL (mg/dl)			
Serum LDL(mg/dl)			
Serum FBS (mmol/L)			
Serum HbA1c (%)			

Modified borg scale:

SCALE	SEVERITY
0	No Breathlessness At All
0.5	Very Very Slight (Just Noticeable)
1	Very Slight
2	Slight Breathlessness
3	Moderate
4	Somewhat severe
5	Severe Breathlessness
6	
7	Very Severe Breathlessness
8	
9	Very Very Severe (Almost Maximum)
10	Maximum

AppendixIII

Standard pharmacotherapy for stable patient of ACO:

(GOLD 2015)

- **Inhaled corticosteroid** (in low or moderate dose, depending on level of symptoms)
- **Inhaled long acting bronchial agonist (LABA), and /or**
- **long acting muscarinic agonist (LAMA)**
- **Advice-**
 - on smoking cessation.
 - Appropriate self management strategies.
 - Regular follow up.

Appendix IV

Cholecalciferol supplementation schedule for D₃ deficient [serum 25(OH)D<30 ng/ml] ACO pts

Our aim is

- to avail (within 6 months) and maintain serum 25(OH)D @ 60-80 ng/ml + serum Ca²⁺ @ 8.5-10.5 mg/ml,
- for having extra-calcaemic effect of vitamin D₃,
- on lungs and other tissues

At 1st visit / at day 0:

Cholecalciferol 80,000 IU (2 capsules of 40,000 IU) / wk, for 12 weeks (3 months)

At 2nd visit / at day 90 / after 3 months:

If, serum 25 (OH)D + serum Ca ²⁺ =	Then, for next 3 months, prescribed dose will be -	So, for next 3 months, dose schedule will be -
30-40 ng/ml + 8.5-10.5 mg/ml	4600 IU/day	4600 IU X 7 = 32,200 IU / 7 days = 1 cap (40,000 IU) / wk
40-50 ng/ml + 8.5-10.5 mg/ml	3000 IU/day	3000 X 15 = 45,000 IU / 15 days = 1 cap (40,000 IU) / 2 wks
60-80 ng/ml + 8.5-10.5 mg/ml	not suggested in guideline, but, to get extra-calcaemic effect of D₃	1 cap (40,000 IU) / 6 wks
> 80 ng/ml + 8.5-10.5 mg/ml	stop taking drug & symptom analysis	no dose for 3 months
>150 ng/ml + >10.5 mg/ml	close monitoring and ask for – 
 • feeling sick or being sick • poor appetite or loss of appetite • feeling very thirsty • passing urine often 	no dose for 3 months

	
• constipation or diarrhea• abdominal pain• muscle weakness• pain• bone pain• feeling confused• feeling tired	
--	---	--

At 3rd visit / at day 180 / after 6 months:

Pt will be referred to physician and will be suggested to follow the above-mentioned schedule

Ref: Vitamin D Council. I tested my vitamin D level. What do my results mean? 2017 [Internet]. [Cited 2018 March 25]. Available from: <https://www.vitamindcouncil.org/i-tested-my-vitamin-d-level-what-do-my-results-mean/>

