For the assessment of all the variables of all the patients on day 0, at 13th week and as well as at 26th week, they will be designated as A₀, A₁ and A₂ (control) and B₀, B₁ and B₂ (study). In addition, for the mean of SpO₂, level of dyspnea and level of fatigue at resting condition (before 6MWT), all the groups will be further designated as A_{0before}, A_{1before}, A_{2before}, B_{0before}, B_{1before} and B_{2before} respectively. Similarly after 6MWT all these six subgroups will be again designated as A_{0after}, A_{1after}, A_{2after} and B_{0after}, B_{1after}, B_{2after}, for measurement of these three variables.

Sample size calculation

Using the following statistical formula

$$n = [(Z\alpha + Z\beta)^2 \times (\sigma_1^2 + \sigma_2^2)] / (\mu_1 - \mu_2)^2$$

(Kirkwood and Sterne 2003)

$$\text{Mean of control, } \mu_1 = 364.1$$

$$\text{Mean of study group, } \mu_2 = 357.3$$

$$\text{SD of control, } \sigma_1 = 7.21$$

$$\text{SD of study group, } \sigma_2 = 12.25$$

(Hassan 2018)

$$\text{Type I Error, } Z\alpha = 1.96$$

$$\text{Type II Error, } Z\beta = 0.84$$

(Kirkwood and Sterne 2003)

Therefore,

$$\begin{aligned} n &= [(Z\alpha + Z\beta)^2 \times (\sigma_1^2 + \sigma_2^2)] / (\mu_1 - \mu_2)^2 \\ &= [(1.96 + 0.84)^2 \times (7.21^2 + 12.25^2)] / (364.1 - 357.3)^2 \\ &= [7.84 \times (51.9841 + 150.0625)] / (6.8)^2 \\ &= 1584.04534 / 46.24 \\ &= 34.2570359 \\ &= \text{approximately 35 for each group.} \end{aligned}$$

Subject selection:

Inclusion criteria

- Pulmonologist diagnosed stable patient of ACO
(GINA and GOLD 2015)
- Duration of ACO: > 4 year
- Vitamin D₃ deficient : Serum 25(OH)D <30 ng/ml
(Vitamin D Council 2017)
- Age: 40 -70 years
- Sex: Male
- Socioeconomic status: middle class
- Smoker
- Anthropometric status:
 - BMI=18.6-24.9 kg/m²
(WHO 2006)
 - mid upper arm circumference>25.1 cm
(Sultana et al. 2015)
 - waist-hip ratio<0.89
(Sultana et al. 2015)
- Serum parathormone: 10-65 pg/ml
- Serum Ca²⁺: 8.5-10.5 mg/dl
- Serum PO₄³⁻: 2.3-4.7 mg/dl
- Serum alkaline phosphatase: 30-120 U/L
- SGPT: <50 U/L
- Serum creatinine: 0.7-1.3 mg/dl
- FBS: 3.5-6.1 mmol/L
- Serum HbA1c: 4.5-6.3 %

- Serum cholesterol: <200 mg/dl
- Serum HDL: >40 mg/dl,
- Serum LDL: <130 mg/dl
- Serum TG: <150 mg/dl

Exclusion criteria

With history of:

[figure not shown]
- any other pulmonary diseases, as,
 - ✓ chronic obstructive pulmonary disease
 - ✓ bronchial asthma
 - ✓ respiratory tract infection
 - ✓ bronchiectasis
 - ✓ pleural effusion
 - ✓ tuberculosis

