If the patient with D₃ deficiency [Serum 25(OH)D <30 ng/ml] and not with renal insufficiency (Serum creatinine >1.3 mg/dl), then the Fasting blood sugar, serum HbA_{1c}, serum parathormone (PTH), serum calcium (Ca²⁺), serum phosphate (PO₄³⁻), serum alkaline phosphatase (ALP), serum SGPT, serum cholesterol, serum High Density Lipoprotein (HDL), serum low density lipoprotein (LDL), serum triglyceride (TG), will be assessed from the preserved blood.

After that their height and weight will be measured and the spirometric lung function test will be done by using a portable spirometer (PONY FX, cosmed, Italy]. After getting all the biochemical and spirometric reports the final selection will be done, according to the inclusion and exclusion criteria. All the eligible patients will be randomly assigned to either 'Control' or 'Study' groups and will be thoroughly informed about the objectives and detailed study procedure, once again.

Subsequently a standard therapeutic treatment (according to GOLD guideline) will be prescribed to all the selected stable ACO patients of both groups. Proper education will be given about drug, method of taking medication and medication plan.

Along with the standard pharmacological treatment of ACO, the patients of the 'Study group' will be prescribed for 80,000 IU/ week of oral vitamin D₃, for consecutive 13 weeks. Subsequently, all the patients will be cordially requested to again visit the Department of physiology, BSMMU, on 13th week of their follow up to reexamine all the study

variables along with serum 25(OH)D and Ca^{2+} (to check the toxicity). These data will be recorded as values of '13th week' (B13).

Then according to serum level of 25(OH)D and Ca^{2+} (American Vitamin D council 2017), 40,000 IU / 1 to 6 week oral vitamin D₃ will be prescribed, for further 13 weeks. At 26th week of follow up, they will be requested again to visit the Department of Physiology, BSMMU, to reexamine all the study variables, and the data will be recorded as values of '26th week' (B26).

Similarly, all the patients of 'control group' will be prescribed for placebo (along with standard pharmacological treatment of ACO, prescribed by pulmonologist) for consecutive 26 weeks and their respective data will be recorded as A13 and A26.

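### Appendix IV prints its serum calcium limits in mg/ml where the rest of the protocol uses mg/dl, so the second-visit dosing and toxicity limits are 100 times too high as written (low severity).

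*Combined protocol and SAP*

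**What the plan says.** Appendix IV holds the supplementation schedule. Its aim statement gives the calcium target as "serum Ca²⁺ @ 8.5-10.5 mg/ml". The table for the second visit pairs a 25(OH)D band with a calcium condition in every row. The first four rows use 8.5-10.5 mg/ml. The last row, which calls for close monitoring and questions about symptoms, reads ">150 ng/ml + >10.5 mg/ml".

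Two other places in the protocol use a different unit for the same analyte. The inclusion criteria state "Serum Ca²⁺: 8.5-10.5 mg/dl". The data schedule in Appendix-II, under haematological variables, labels the field "Serum Ca ² (mg/dl)" for all three measurement days.

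The Study procedure section makes the Appendix IV limits operative. At the 13th-week visit patients are re-examined on the study "variables along with serum 25(OH)D and Ca^{2+} (to check the toxicity)". The dosing rule for the next 13 weeks then opens "Then according to serum level of 25(OH)D and Ca^{2+}", and Appendix IV is where the limits for that rule are set out.

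**The concern.** These limits are decision thresholds. They govern what happens to a patient halfway through the trial, and one of them marks the row for suspected toxicity. A threshold printed in the wrong unit, in the one table that states it, leaves the written rule impossible to follow as it stands. Staff must correct it themselves by reference to another section.

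The schedule may also be used outside the trial team. Appendix IV says that after six months the patient goes to a physician and is advised to keep to the same schedule. If that physician were given only the appendix, the mg/dl entries in the inclusion criteria and on the data form would not be to hand. The documents do not say what the physician receives, so this is a reason for tidiness and not evidence of harm.

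**Working it through.** **Inputs**

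| Place | Calcium limit as printed |
|---|---|
| Inclusion criteria | 8.5-10.5 mg/dl |
| Appendix-II data form | unit mg/dl |
| Appendix IV, aim | 8.5-10.5 mg/ml |
| Appendix IV, 30-40 ng/ml row | 8.5-10.5 mg/ml |
| Appendix IV, 40-50 ng/ml row | 8.5-10.5 mg/ml |
| Appendix IV, 60-80 ng/ml row | 8.5-10.5 mg/ml |
| Appendix IV, >80 ng/ml row | 8.5-10.5 mg/ml |
| Appendix IV, >150 ng/ml row | >10.5 mg/ml |

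1. Count of affected places: 1 (aim) + 4 (rows at 8.5-10.5) + 1 (row at >10.5) = 6.
2. Conversion: 1 dl = 100 ml, so 1 mg/ml = 100 mg/dl.
3. Printed limits in the protocol's own unit: 8.5 × 100 = 850 mg/dl and 10.5 × 100 = 1,050 mg/dl. The ratio to the inclusion range is 850/8.5 = 1,050/10.5 = 100.
4. Inclusion range in the printed unit: 8.5/100 = 0.085 mg/ml and 10.5/100 = 0.105 mg/ml.
5. Distance from the table: 8.5/0.105 = 80.95. A patient at the top of the inclusion range is about 81-fold below the lowest printed limit. Twice that calcium value, 21 mg/dl or 0.21 mg/ml, would still be far below the last row's limit of 10.5 mg/ml.
6. After replacing mg/ml with mg/dl, five places read 8.5-10.5 mg/dl and one reads >10.5 mg/dl. These agree with the inclusion range and with the unit on the data form.

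**Could this come from reading the PDF?** That is unlikely. The unit is the same in all six places, and mg/dl was read correctly for calcium in both other sections.

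**Does calcium change a printed dose?** The first four rows share one calcium range, so 25(OH)D alone separates them. The last two rows both withhold the drug for three months. Calcium therefore separates no two printed doses, although it forms part of the row that calls for close monitoring.

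**The case against.** The best counter-argument is that this is a self-evident slip without consequence. The figures match the inclusion range digit for digit, and the form on which calcium is recorded already says mg/dl. Staff would compare an mg/dl result with 8.5-10.5 and reach the intended row. No endpoint, analysis or sample size depends on it. All of this stands, and it is why the severity is low. It does not remove the point: the threshold is wrong in operative text, and the correction is unambiguous.

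A reader might go further and infer that no patient could be dosed in the second phase, or that toxicity would be missed. That follows only if someone applies mg/ml literally, and the documents give no reason to expect it. The 81-fold figure describes the size of the slip and is not a measure of risk.

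A reader might also see an arithmetic error in the 30-40 ng/ml row, "4600 IU X 7 = 32,200 IU / 7 days = 1 cap (40,000 IU) / wk", because 32,200 is not 40,000. The documents do not support that. The daily dose and the capsule schedule stand in separate columns, and the row openly states one 40,000 IU capsule weekly, so the dose delivered is given.

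It is also fair to say that correcting the unit does not complete the table. For example, no printed row covers calcium above 10.5 with 25(OH)D at or below 150 ng/ml. That is a separate matter from the unit.

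**Conclusion.** The point holds as a unit error of a factor of 100 in six places in Appendix IV, within the table that serves as the second-visit dosing and toxicity rule. As printed, the calcium limits cannot be applied literally. Severity is low: the intended unit is evident from the inclusion criteria and the data form, and no dosing error is shown.

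The conclusion rests on one assumption, that mg/dl is the intended unit. The identical figures in the inclusion criteria and the mg/dl label on the form support it strongly. This is an inconsistent unit label; no calculation in the plan is wrong because of it, and no effect on the trial's results is claimed.

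**What to change.** In Appendix IV, change mg/ml to mg/dl for calcium in all six places: 8.5-10.5 mg/dl in the aim and the first four rows, and >10.5 mg/dl in the last row. Capsules, doses, visits and analysis do not change. The only cost is that the corrected appendix may need to be filed with the ethics committee.

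Optional, and not part of this point: the Appendix-II form labels 25(OH)D and phosphate in mg/ml, where the inclusion criteria use ng/ml and mg/dl. Each label appears only once, in a table that was imperfectly read from the PDF, so check them against the source document before changing them.

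### At week 13, Appendix IV acts on calcium above 10.5 only if 25(OH)D also exceeds 150 ng/ml; hypercalcaemia at 150 or below has no stated action

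*Combined protocol and SAP*

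**What the plan says.** The Project Summary and the Study procedure section have patients re-examined at week 13 "along with serum 25(OH)D and Ca^{2+} (to check the toxicity". The second-half dose is then to follow from the two results: "40,000 IU / 1 to 6 week oral vitamin D₃ will be prescribed, for further 13 weeks".

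Appendix IV gives the detail. Its aim is "to avail (within 6 months) and maintain serum 25(OH)D @ 60-80 ng/ml", together with calcium of 8.5-10.5. Its day-90 table pairs a 25(OH)D band with a calcium band in each row. The row for patients already at target is "60-80 ng/ml + 8.5-10.5 mg/ml" and gives one capsule every 6 weeks. The first stop row is "> 80 ng/ml + 8.5-10.5 mg/ml". The last row, which carries the list of toxicity symptoms and also gives no dose, is ">150 ng/ml + >10.5 mg/ml". At day 180 the same table is handed on: "Pt will be referred to physician and will be suggested to follow the above-mentioned schedule".

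The haematology form in Appendix II schedules calcium on days 1, 90 and 180 only.

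**The concern.** The row meant to catch toxicity needs two abnormal results at once, and its 25(OH)D threshold is far above the level the trial aims for. Raised calcium is a reason for action in its own right, yet the table recognises it only in a patient whose 25(OH)D is also above 150 ng/ml.

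The result is out of order. At 120 ng/ml a patient with normal calcium is stopped, while a patient at the same level with raised calcium, who is worse off, is not covered.

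At stake is the safety of patients in the vitamin D arm. Day 90 is the only scheduled on-treatment calcium result that can still change a trial dose; the next is at day 180, when dosing ends. Because patients are then referred to the same table, the gap goes with them.

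**Working it through.** There is no published figure to reproduce. The check is whether the table covers the results it may meet.

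**Step 1: the rows as conditions.** The plus sign is read as *and*. The column header pairs the two assays in this way, and the stated aim pairs its two targets in the same way.

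| 25(OH)D, ng/ml | Calcium required | Second-half dose |
|---|---|---|
| 30-40 | 8.5-10.5 | 1 capsule a week |
| 40-50 | 8.5-10.5 | 1 capsule per 2 weeks |
| 60-80 | 8.5-10.5 | 1 capsule per 6 weeks |
| above 80 | 8.5-10.5 | none |
| above 150 | above 10.5 | none |

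**Step 2: coverage when calcium is high.** Every whole-number 25(OH)D from 0 to 150 was tested against calcium from 10.6 to 16.0 in steps of 0.1. The number of combinations matching any row was 0. At calcium 11, for example, 25(OH)D of 35, 70, 90, 120 and 150 match nothing; 151 and 200 match the last row.

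**Step 3: the more generous reading.** Suppose the stop above 80 applies whatever the calcium. Then 90, 120 and 150 are covered at calcium 11. 35 and 70 are not, so the whole 60-80 target range remains open.

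**Step 4: distance from the target.** 150 / 80 = 1.875, so the written calcium action starts at nearly twice the top of the target.

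**Step 5: other stopping rules in the available text.** There are three: voluntary withdrawal and failure to follow the procedure (both under Study procedure), and symptoms during the walk test. None refers to calcium.

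**Step 6: doses involved.** Exposure before the check is 80,000 x 12 = 960,000 IU on Appendix IV's 12 weeks, or 80,000 x 13 = 1,040,000 IU on the main text's 13. If a hypercalcaemic patient within the 60-80 target were nevertheless kept on capsules, with the first at the visit, he would take 3 in 13 weeks: 3 x 40,000 = 120,000 IU. Weekly capsules would give 13 x 40,000 = 520,000 IU, but that schedule is for 25(OH)D of about 40 or below.

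**Units.** Appendix IV prints calcium in mg/ml. The inclusion criterion, "Serum Ca²⁺: 8.5-10.5 mg/dl", shows that mg/dl is meant. This is a typing slip to correct when the row is rewritten, and nothing above depends on it.

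**The case against.** The strongest reply is that the table is silent on these patients and does not tell anyone to go on dosing. That stands. A reader might infer that a patient at 70 ng/ml with calcium 11 must continue because his 25(OH)D band carries a dose. The documents do not support this: every row that gives a capsule requires calcium of 8.5-10.5, and keeping calcium in that range is part of the stated aim.

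It is also fair that the main text's 1-to-6-week range summarises a table with two no-dose rows, so it should not be read as forbidding a stop. It still supplies no calcium threshold.

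A clinician would very probably apply the stop above 80 to a patient with high calcium as well. That narrows the practical gap to 80 ng/ml or below but does not close it.

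The protocol provides telephone and home follow-up, and the good clinical practice principles in Appendix V put safety first and leave medical decisions to a qualified physician. These make unthinking continuation less likely, but neither is a calcium rule.

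The Rationale calls the schedule safe because the toxic dose is put at 50,000 IU a day for several months. The first-half dose averages 80,000 / 7 = 11,429 IU a day, about 23% of that. This bears on how often hypercalcaemia would occur. It does not bear on what to do when it does, and the plan itself thought the calcium check necessary.

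**Conclusion.** The point holds as a safety gap that should be fixed. As written, calcium above 10.5 has a stated action only when 25(OH)D exceeds 150 ng/ml. On the most generous reading of the stop above 80, hypercalcaemia at or below 80, target range included, still has none.

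The conclusion rests on reading the plus sign as *and*, and on the available text; Appendix I was not available, and a calcium rule there would change the conclusion.

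The number of patients affected cannot be given. The documents contain no week-13 calcium or 25(OH)D distribution, and any count would depend on a spread and a mean shift with no source in them. A reader might also infer that the gap biases the comparison of groups A and B. Nothing in the documents shows that.

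**What to change.** Replace the last row of the day-90 table with a calcium-only row, applied in both arms:

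*Serum calcium >10.5 mg/dl at any 25(OH)D: withhold capsules, ask about the listed symptoms, repeat calcium in about 2 weeks; if still raised, no further dose and refer.*

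Withholding until a repeat avoids ending treatment for the whole second half on one unconfirmed value. The row needs neither the 25(OH)D result nor the allocation, so it can be used in the placebo arm without unblinding.

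Make the stop above 80 ng/ml apply whatever the calcium, keeping its symptom enquiry. Print calcium in mg/dl throughout the table. State in the Project Summary and the Study procedure section that the second-half dose may be none. The day-180 referral then inherits the corrected table.

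The cost is one amended table, matching wording in two places, and one repeat blood test for each hypercalcaemic patient. Some of those patients may receive less vitamin D than they otherwise would, which is the price of the safeguard. No extra patients are needed.

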Therefore, on the basis of this background the present study has been designed to evaluate the effects of Vitamin D₃ on the spirometric lung function status, exercise tolerance in D₃ deficient, stable patients with ACO. This study may draw attention of the physicians about the beneficial effects of the vitamin D₃ on both pulmonary and extrapulmonary manifestation in ACO patients.

Rationale

In recent years, ACO has gained much attention and have extensively reviewed worldwide. There is a scarcity of population-based data on ACO in Bangladesh except Habib et al. As patients with ACO seem to be at risk for a poor outcome, high risk of exacerbations, it is of utmost importance to perform more research on this significant disease.

However, as far as it has been searched association of vitamin D status with ACO has only seen by Odler et al. (2015) who reported significant decrement of serum 25(OH)D in elderly ACO patients. Strikingly no study have been conducted to observe the effects of this fat soluble vitamin on lung function and exercise capacity in vitamin D₃ deficient, stable patients with ACO.

To the best of our knowledge, as far as we reviewed with a loading dose followed by upto 50,000 IU/week of oral D₃ for 12 weeks, could not improve the spirometric variables in stable COPD patients (Said and Elnaeem 2014; Hornikx et al. 2015; Moosavi and Shoushtari 2015; Rezk et al. 2015). Whereas, Nazarian et al. (2011) found significant improvement of insulin sensitivity in patients with Type II Diabetes meliitus after 4 weeks oral supplementation of 10,000IU/day vitamin D₃ (Nazarian et al. 2011). On the basis of this observation, we have selected 80,000 IU/ week of oral vitamin D₃ , for consecutive 13 weeks followed by 40,000 IU / 1 to 6 week for further consecutive 13 weeks, as the dosage schedule for our D₃ deficient patients of stable ACO. In addition,

as toxicity dose of vitamin D₃ is very high (50,000IU/day for several months) (Veith 1999), this dose schedule will be safe for our patients.

Therefore, on the basis of this background the present study has been designed to evaluate the effects of Vitamin D₃ on the spirometric lung function status, exercise tolerance in D₃ deficient, stable patients with ACO. This study may draw attention of the physicians about the beneficial effects of the vitamin D₃ on both pulmonary and extrapulmonary manifestation in ACO patients.

Research question

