With these, all patients of both the groups will be advised to continue ad lib (according to their own choice) diet as well as to have sunlight exposure (within 10 am to 2 pm) only for 20 minutes daily (Manjeeta 2016).

In the mean time, a good rapport will be built up to take time to time follow-up over telephone and visiting patient's place with scheduled appointment to maintain a proper follow up at 1st (day 1) 2nd (at 13th week) and 3rd (at 26th week) visit of the study , in addition to the hematological values.

Any patient, who will be failed to follow the study procedure exactly during study period, will be dropped and a new one will be included to fulfill the desired total sample number.

Test procedure for spirometry

(Hassan 2018)

- At first, the subject will be asked to take rest sitting on a chair and remain calm and quiet for 5 minutes.
- The detailed procedure will be explained to him to ensure his maximum cooperation.
- The switch of spirometer will be on and windows will be open.
- Patients' information will be filled up and saved.
- The patient will be asked to hold a disposable paper mouthpiece (connected to spirometer) in his hand horizontally and to place it in between his two lips.
- To make good seal, he will also be asked to put the lips tightly around the outside of the mouthpiece.
- Then he will be asked to inhale first as deeply and as rapidly, as possible, which was followed by a forceful expiration for the possible longest period into the mouthpiece.
- The readings of different variables will be recorded from the spirometer monitor.
- Three (3) consecutive readings at 5 minutes interval for each parameter will be taken and the best value will be noted.

Test procedure for pulse oximetry

(Hassan 2018)

- The patient will be asked to take rest and remain calm and quiet for 10 minutes (MacAllister et al. 2007).
- The detailed procedure will be explained to him to ensure his maximum cooperation.
- Then his right index finger will be washed with alcohol and pulse oximeter sensor will be applied.
- The switch button will be on.
- The reading will be recorded from the display screen.
- Three (3) consecutive readings at 5 minutes interval will be taken and the best value will be noted.

Procedure for six minute walk test (6MWT)

(Hassan 2018)

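### Toxicity symptoms are asked about only at day 90 and only at high 25(OH)D levels, so symptom data have no control group; laboratory safety is measured in both arms, but no safety summary by arm is planned.

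*Combined protocol and SAP*

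**What the plan says.** **Symptom enquiry.** The day-90 table in Appendix IV has two rows that call for it. Above 80 ng/ml with calcium in the 8.5-10.5 band, the action is "stop taking drug & symptom analysis". In the row headed ">150 ng/ml + >10.5 mg/ml", the action is "close monitoring and ask for", followed by 11 listed items such as nausea, thirst, frequent urination, constipation, bone pain, confusion and tiredness. The other rows ask nothing about symptoms. At day 180 the appendix provides only for referral to a physician and advice to follow the same schedule.

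**Who can reach those rows.** Entry requires "Serum 25(OH)D <30 ng/ml" (inclusion criteria). Controls receive placebo for 26 weeks.

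**Laboratory safety.** The Study procedure has patients return at week 13 to re-examine the study "variables along with serum 25(OH)D and Ca^{2+} (to check the toxicity"). For the control group, "their respective data will be recorded as A13 and A26". The data schedule (Appendix II) is common to both arms and lists calcium, phosphate, PTH, creatinine and SGPT at days 1, 90 and 180.

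**Other symptom fields.** The data schedule also records dyspnea and fatigue scores before and after the walk test at days 0, 90 and 180, together with symptoms at the end of exercise.

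**Safety statement and analysis.** The Rationale says that "this dose schedule will be safe for our patients", resting on a cited toxicity dose. The Statistical Analysis section lists t tests, one-way ANOVA and Pearson correlation, and names no safety summary.

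**The concern.** Whether a patient is asked about toxicity symptoms depends on a 25(OH)D level measured after randomisation, and that level is what the treatment is meant to change. The result is a symptom count from selected patients who should all be in one arm. Tiredness, poor appetite, constipation and thirst also occur without vitamin D, so such a count cannot be read as an effect of treatment.

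The gap also affects the vitamin D arm itself. Appendix IV aims for 60-80 ng/ml, and patients who reach that range are asked nothing. Nor are patients below it. The second 13 weeks of treatment end with no symptom enquiry. The data schedule has no toxicity-symptom or general adverse-event field, so there is no designated place for a complaint that a patient volunteers.

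At stake is whether the trial can report how this high-dose regimen was tolerated compared with placebo. Symptoms not asked about during follow-up cannot be reliably recovered afterwards.

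**Working it through.** **1. Who is asked about toxicity symptoms, under the plan as written**

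| Source of information | Vitamin D arm | Control arm |
|---|---|---|
| Symptom analysis, day 90 | only above 80 ng/ml | none expected |
| Itemised list, day 90 | only above 150 ng/ml with calcium above 10.5 | none expected |
| Toxicity symptoms, day 180 | none set | none set |
| Calcium, creatinine, SGPT, PTH, phosphate | days 1, 90, 180 | days 1, 90, 180 |
| Borg dyspnea and fatigue, end-of-exercise symptoms | days 0, 90, 180 | days 0, 90, 180 |
| Safety summary by arm | not specified | not specified |

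A control would have to rise from below 30 ng/ml to above 80 ng/ml on placebo. The documents give no figure for change on placebo, and both arms are advised 20 minutes of daily sun, so this is an inference, though a strong one. The expected number of controls asked is about 0 of 35 (or 0 of 30), and a symptom risk difference cannot be estimated.

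The two conditions of the itemised list must hold together. The table has no row for calcium above 10.5 with 25(OH)D at or below 150 ng/ml, and none for below 30 or 50-60 ng/ml. It also prints calcium in mg/ml where the inclusion criteria use mg/dl. These passages need to be reconciled. No rule is proposed here.

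**2. Number per arm**

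The plan states no figure for safety, so the only figure to reproduce is its sample size:

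n = (1.96 + 0.84)² × (7.21² + 12.25²) / (364.1 − 357.3)² = 1584.05 / 46.24 = 34.26, rounded up to 35.

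This reproduces. The Methods table gives 30 per group instead, so both are carried forward.

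**3. What asking everyone would give**

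One-sided 95% upper bound when no event is seen in an arm, 1 − 0.05^(1/n):

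- n = 35: 1 − 0.05^(1/35) = 8.2%
- n = 30: 1 − 0.05^(1/30) = 9.5%

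Vitamin D arm rate needed for 80% power at two-sided 5% (normal approximation, pooled variance under the null). The placebo rates are assumed, since the documents give none:

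| Assumed placebo rate | 35 per arm | 30 per arm |
|---|---|---|
| 5% | 30% | 33% |
| 10% | 38% | 41% |
| 20% | 52% | 54% |

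The approximation is optimistic at low rates: for 5% against 30%, Fisher's exact test has 74% power with 35 per arm and 63% with 30. For 5% against 15%, its power is 14% and 9%.

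**4. What the laboratory data already allow**

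The standardised difference detectable with 80% power is 2.80 × √(2/n):

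- n = 35: 2.80 × √(2/35) = 0.67 SD
- n = 30: 2.80 × √(2/30) = 0.72 SD

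A comparison of calcium or creatinine between arms is therefore feasible for large differences, although the plan does not name it as a safety analysis.

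**The case against.** The strongest reply is that the plan's toxicity check is a laboratory one and it covers both arms. Calcium is measured at week 13 expressly for that purpose, creatinine and SGPT are on the common data sheet, and the general between-group t test can be applied to them. That stands. A reader might infer from the symptom gap that the trial has no controlled safety data at all. The documents do not support that: the missing control group concerns toxicity symptoms only. Tiredness is also partly covered by the fatigue score taken before the walk test.

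A reader might also infer that the trial sets out to prove safety and cannot. The Rationale sentence is a justification of dose, and no objective or hypothesis concerns safety, so the plan does not fail a test that it proposed.

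Next, Appendix IV is a supplementation schedule, not an adverse-event plan, and the Study procedure provides for "time to time follow-up over telephone" and home visits, where symptoms may come up. So it would be too strong to say that other patients are never asked. The fair statement is that nothing specifies it and no form field receives it. Some pages between the analysis section and Appendix II were not in the text available, so a provision there cannot be excluded.

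Finally, 30-35 per arm would miss a modest excess even with complete questioning. That is correct, and it limits what the remedy can claim. It does not justify asking one arm only.

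**Conclusion.** The point holds for toxicity symptoms. As specified, they are sought once, at day 90, in patients selected by a level that controls are not expected to reach. The resulting data have no comparator, leave out vitamin D patients at or below 80 ng/ml, and stop before day 180. Laboratory values and Borg scores are collected in both arms, but no safety summary by arm is planned for them.

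The size is structural: about no controls asked, hence no symptom risk difference. How many vitamin D patients would pass 80 ng/ml is not stated, so no bound is given for that subgroup. The conclusion rests on controls staying below 80 ng/ml and on there being no adverse-event provision in pages not available for review.

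This is a worthwhile, low-cost improvement to data collection and reporting. It does not bear on the efficacy analysis.

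**What to change.** - **Collection.** Put the symptom list already printed in Appendix IV, with one open adverse-event question, to every patient in both arms, in the same words, at weeks 13 and 26 and at the planned telephone contacts. Ask regardless of 25(OH)D level.
- **Form.** Add the matching fields to the data schedule.
- **Analysis.** State in the Statistical Analysis section that symptoms, adverse events and calcium above 10.5 mg/dl will be tabulated by arm. Present the table as descriptive, and say that with 30-35 per arm only large excesses could be detected.

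The cost is one form page and a few minutes per visit, with no new visit or test. The dosing and monitoring rules of Appendix IV are left as they are.
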